4.1.3 Dosing Administration and Schedule

A treatment schedule is provided in Appendix C. Avelumab will be administered via IV infusion over 60 minutes (+/- 10 minutes). Trabectedin is given as an outpatient 24-hour infusion by pump. During week 1, subjects will receive both drugs: avelumab followed by the standard 24-hour infusion of trabectedin. Following avelumab infusions, subjects must be observed for 60 minutes ± 10 minutes (Cycle 1) or 30 minutes ± 5 minutes (Cycle 2+) post-infusion, prior to beginning trabectedin, for potential infusion-related reactions.

Avelumab will be administered every 2 weeks. Trabectedin will be administered every 3 weeks for the first two doses (Week 1 and Week 4), and then every four weeks (Week 7, Week 11,...) moving forward. After Cycle 2 of trabectedin, dosing may extend to every 5 weeks at investigator discretion, for management of trabectedin-associated toxicity only. Delays of trabectedin beyond 5 weeks may be allowed but require written approval from the Sponsor-Investigator.

It should be noted that trabectedin has significant single agent toxicity. Treatment schedule and evaluation of toxicity are discussed in **Section 7.0**.

4.1.4 Assessment of Response and duration of therapy

Subjects will have their first post-treatment scan during week 12 and every 12 weeks after that. Additional scans may be ordered at the discretion of the treating physician, if clinically indicated. If any non-protocol scans are collected, a RECIST 1.1 read should be obtained. Response assessment will be based on RECIST 1.1. Subjects who are demonstrating CR must be treated for at least 12 weeks after CR was confirmed (2nd scan with CR). Subjects confirmed to have a CR who have been taken off treatment will continue to be followed on study and monitored radiographically every 12 weeks for up to 2 years. Upon relapse they may be re-treated with trabectedin and avelumab.

It is possible that a subject may become surgically resectable during the course of treatment. Subjects who are rendered no evidence of disease via a surgical intervention after successful combination therapy should be treated just as if they had a CR in response to the medication. These subjects will receive an additional 12 weeks of protocol therapy post-surgery, and will be followed on study and monitored radiographically every 12 weeks for up to 2 years. Upon relapse, they may be re-treated with trabectedin and avelumab.

Subjects with an unconfirmed or equivocal progression of disease may continue trial treatment until progression is confirmed by repeat CT/MRI, 6 weeks later. Subjects may continue protocol therapy until a confirmation scan is obtained, or until symptomatic progression or clinical decline. Subjects may only continue to receive study treatment while waiting for confirmation of PD if the following criteria are met:

- No significant decline in ECOG performance status in the opinion of the treating investigator
- Absence of rapid progression of disease in the opinion of the treating investigator
- Absence of progressive tumor at critical anatomical sites (e.g. cord compression) requiring urgent alternative medical intervention

4.2 Estimated Accrual

- **Phase 1:** 6 subjects, may expand up to 18
- **Phase 2:** 16 subjects

A minimum of 22, and up to a possible total of 34 subjects are anticipated to receive treatment.

5.0 SUBJECT ELIGIBILITY

5.1 Inclusion criteria:

1. Subjects, ≥ 18 years old, must have a histologically confirmed diagnosis of advanced (metastatic or unresectable) soft tissue sarcoma with one of the following subtypes:
 - a. Leiomyosarcoma
 - b. Liposarcoma
2. Subject must be clinically indicated to receive trabectedin therapy as part of routine care. Subjects may be first line, or have received any number of prior systemic therapies.
3. Subjects must have adequate organ function and blood chemistry and blood count parameters as defined below. Transfusion is permitted as clinically indicated.
 - a. Total bilirubin ≤ 1.5 x upper limit of normal (ULN) mg/dL
 - b. AST ≤ 2.5 x ULN and ALT ≤ 2.5 x ULN
 - c. Alkaline Phosphatase < 2.5 x ULN
 - d. Serum creatinine ≤ 1.5 x ULN
 - e. Calculated creatinine clearance ≥ 30 mL/min using the Cockcroft-Gault formula may be included)
 - f. Creatinine phosphokinase (CPK) ≤ 2.5 x ULN
 - g. Absolute neutrophil count (ANC) $\geq 1.5 \times 10^9/L$;
 - h. Platelet count $\geq 100,000/mm^3$ ($100 \times 10^9/L$);
 - i. Hemoglobin ≥ 9 g/dL
4. Subjects must demonstrate a left ventricle ejection fraction (LVEF) of $> 45\%$ by ECHO or MUGA.
5. Male or non-pregnant and non-breast feeding female:
 - a. Females of child-bearing potential must agree to use highly effective contraception without interruption from initiation of therapy and while on study medication and have a negative serum pregnancy test (β - hCG) result at screening and agree to ongoing pregnancy testing during the course of the study, and at the end of study treatment. A highly effective method of contraception is defined as one that results in a low failure rate (that is, $< 1\%$ per year), when used consistently and correctly, such as implants, injectables, combined oral contraceptives, some intrauterine contraceptive devices, sexual abstinence, or a vasectomized partner (Appendix C).
 - b. Male subjects must practice abstinence or agree to use a condom during sexual contact with a pregnant female or a female of childbearing potential while participating in the study (Appendix C).
6. All ongoing toxicities related to prior therapies must be resolved to Grade 1 or better (except alopecia).
7. Subjects must have an ECOG performance status ≤ 1 or Karnofsky performance scale ≥ 70 (see Appendix A and B).
8. Subjects must have one or more measureable lesions, as determined by RECIST v1.1 assessed by CT or MRI.
9. Subjects must have a life expectancy of ≥ 6 months, as determined by the treating physician.
10. Ability to understand and sign informed consent document.
11. Willingness and ability to comply with the scheduled visits, laboratory tests, and other study procedures.

5.2 Exclusion criteria:

Subjects are not eligible for the trial if they fulfill any of the following exclusion criteria:

1. Known active, uncontrolled, or symptomatic central nervous system (CNS) metastases. A subject with controlled and asymptomatic CNS metastases may participate in this study. As such, the subject must have completed any prior treatment for CNS metastases ≥ 28 days (including radiotherapy and/or surgery) prior to the start of treatment in this study and should not be receiving chronic corticosteroid therapy in excess of 10 mg daily prednisone (or equivalent) for CNS metastases. Subjects with known CNS metastases must be confirmed radiographically stable by at least one imaging study, at least 28 days from last treatment.

2. Receipt of any type of cytotoxic, biologic, or other systemic anticancer therapy (including investigational) within 2 weeks of enrollment.
3. Prior organ transplantation, including allogeneic stem-cell transplantation.
4. Prior treatment with trabectedin.
5. Significant acute or severe chronic infections including, among others:
 - Known history of testing positive test for human immunodeficiency virus (HIV) or known acquired immunodeficiency syndrome (AIDS)
 - Known active infection with Hepatitis B or Hepatitis C.
6. Active autoimmune disease that might deteriorate when receiving an immunostimulatory agent:
 - a. Subjects with diabetes type I, vitiligo, psoriasis, hypo- or hyperthyroid disease not requiring immunosuppressive treatment are eligible
 - b. Subjects requiring hormone replacement with corticosteroids are eligible if the steroids are administered only for the purpose of hormonal replacement and at doses ≤ 10 mg or 10 mg equivalent prednisone per day
 - c. Administration of steroids through a route known to result in a minimal systemic exposure (topical, intranasal, introocular, or inhalation) are acceptable
7. Known severe hypersensitivity reactions to monoclonal antibodies (Grade ≥ 3 NCI-CTCAE v 5.0), any history of anaphylaxis, or uncontrolled asthma (that is, 3 or more features of partially controlled asthma)
8. Pregnant or lactating females.
9. Known, active alcohol or drug abuse.
10. All other significant diseases (for example, inflammatory bowel disease, uncontrolled asthma), which, in the opinion of the Investigator, might impair the subject's tolerance of trial treatment.
11. Any vaccination within 4 weeks of the first dose of avelumab, with the following exceptions:
 - a. Administration of inactivated vaccines, including inactivated flu vaccines, are allowable. However, they should not be given within 2 weeks prior to starting study treatment.
12. Clinically significant cardiovascular disease including cerebral vascular accident/stroke (<6 months prior to enrollment), myocardial infarction (<6 months prior to enrollment), congestive heart failure with NYHA class II or greater or serious cardiac arrhythmia requiring medication.
13. Severe (requiring active treatment) acute or chronic medical conditions including: colitis, inflammatory bowel disease, pneumonitis, or pulmonary fibrosis.
14. Recent (within the past year) or active suicidal ideation or behavior.

6.0 SUBJECT REGISTRATION

Each subject who enters into the screening period for the study receives a unique subject identification number before any study-related procedures are performed. The subject identification number will be assigned. This number will be used to identify the subject throughout the clinical study and must be used on all study documentation related to that subject.

The subject identification number must remain constant throughout the entire clinical study; it must not be changed after initial assignment, including if a subject is rescreened.

A subject is considered enrolled when the investigator decides that the subject has met all eligibility criteria. The investigator is to document this decision and date, in the subject's medical record and in/on the electronic case report form (eCRF).

7.0 TREATMENT PLAN

7.1 Treatment Plan

Trabectedin is given every three or four weeks (Cycle 1 and Cycle 2 Q3W, and then Q4W for Cycle 3+) and avelumab is given every two weeks. During week 1, subjects will receive avelumab followed by a 24 hour infusion of trabectedin afterwards. Trabectedin should be administered on a Q3W schedule for Cycle 1 and Cycle 2. Starting at Cycle 3, trabectedin will be administered on a Q4W schedule, to coincide with avelumab dosing. For toxicity management after Cycle 2, trabectedin administration may delay to Q5W, as clinically indicated for toxicity management only. Delays of trabectedin beyond 5 weeks may be allowed but require written

approval from the Sponsor-Investigator. On days where both drugs are scheduled to be administered, avelumab will be administered first.

Avelumab is administered as a 60 minute IV infusion at a flat dose of 800 mg, diluted with either a 0.9% or 0.45% saline solution. In order to mitigate infusion-related reactions, subjects should be premedicated with an antihistamine and paracetamol (e.g., 25-50 mg diphenhydramine and 500-650 mg paracetamol [acetaminophen] IV or oral equivalent)) within 30-60 minutes prior to the first four (4) doses of avelumab. Premedication may be discontinued for Cycle 5 and beyond of avelumab, at the investigator's discretion. If any infusion-related reaction occurs, the premedication should immediately be reinstated for all cycles of avelumab.

For Cycle 1, avelumab will be given first over 60 minutes (+/- 10 minutes), followed by a 60 minute observation period (+/- 10 minutes). For Cycle 2 and beyond, the post-avelumab observation period will be 30 minutes (+/- 5 minutes). Following completion of the avelumab infusion and observation period, the trabectedin pump will be connected and started. Trabectedin should start within 3 hours (+15 minutes) after the end of the avelumab infusion, but not prior to the end of the observation period post-avelumab dose. Subjects will return to clinic 24 hours later to have the pump disconnected.

Trabectedin is administered by a pump which is calibrated to provide the full, correct dose and rate regardless of whether the pump is actually disconnected at 24 hours or after 24 hours. Every attempt should be made to disconnect the trabectedin as close to 24 hours after starting the infusion as possible, however delays in disconnection will not constitute a protocol deviation. Avelumab infusion will occur over 1 hour, with a +/- 10 minute window.

Trabectedin is a moderately emetogenic chemotherapy and anti-emetics should be given according to standard of care.

Dexamethasone 20 mg IV is recommended as per the trabectedin package insert and should be given 20-30 minutes before trabectedin. Dexamethasone premedication should not be administered until after the 60 minute observation period in Cycle 1, and not until the avelumab infusion has been completed for Cycle 2+ on days where both avelumab and trabectedin are to be administered. Alterations to the dexamethasone are strongly discouraged as dexamethasone does not only function as an anti-emetic, it also may prevent serious toxicities of trabectedin including liver toxicity. Alterations could be considered for extenuating circumstances with Sponsor-Investigator approval. Outside of this pre-medication recommended in the trabectedin package insert, corticosteroids use is discouraged when not absolutely necessary and is not allowed for the treatment of trabectedin associated nausea and vomiting unless the subject has tried and failed to control their nausea with 2 prior anti-emetic regimens.

7.2 Administration of agents

Drug	Dose/ Potency	Dose Frequency	Route of Administration	Regimen/ Treatment Period	Use
Avelumab	800 mg flat dose	Q2 Weeks	60 minute (+/- 10 min) IV infusion	Every 2 weeks, regardless of trabectedin dosing	Experimental
Trabectedin	1.5 mg/m ² , 1.2 mg/m ² , or 1.0 mg/m ²	Q3 Weeks (Cycle 1 and 2) Q4 Weeks (Cycle 3+)	24 hour IV infusion	Day 1 of each cycle*	Standard

*Cycles may be adjusted to q5 weeks, or greater with Sponsor-Investigator approval. No schedule adjustments are permitted until after Cycle 2 of trabectedin is administered.

7.3 Drug Product Information

Avelumab will be provided by EMD Serono. The active pharmaceutical ingredient in avelumab drug product is a fully human antibody (calculated molecular weight of 143832 Dalton) of the immunoglobulin G (IgG) 1 isotype that specifically targets and blocks PD-L1, the ligand for PD-1. Avelumab drug product is a sterile, clear, and colorless concentrate for solution intended for intravenous (IV) infusion. The drug is presented at a concentration of 20 mg/mL in single-use glass vial containing 200 mg of

avelumab. Avelumab drug product must be stored at 2°C to 8°C until use, and it must not be frozen. Vigorous shaking of avelumab product must be avoided. Avelumab drug product must be diluted with 0.9% saline solution; alternatively a 0.45% saline solution can be used if needed. It is recommended that the diluted avelumab solution is used immediately.

A pharmacy manual will contain details regarding administration and preparation of avelumab.

Trabectedin will be stored, prepared, and administered per institutional and FDA-approved product labeling guidelines. Trabectedin will be obtained commercially as this is an FDA approved product.

7.4 Schedule of Treatment Visits

Avelumab will be administered every two weeks starting at Week 1. Dosing may be delayed in response to certain toxicities, as described under Section 10.

Trabectedin will be given every three weeks for Cycle 1 (Week 1) and Cycle 2 (Week 4), and then will be given every 4 weeks (Week 7, Week 11,...). For toxicity management after Cycle 2 (Week 4) Day 1, trabectedin administration may delay to Q5W, as clinically indicated for toxicity management. Delays of trabectedin beyond 5 weeks may be allowed but require written approval from the Sponsor-Investigator.

Administration of either study drug may vary ± 3 days from planned date.

The administration of study drugs during the first 12 weeks (first response assessment timepoint), assuming no dose delays or modifications due to toxicity, is shown below.

The study calendar will be managed in Weeks, with each dose of each drug being noted by a Cycle. For example, assuming there are no deviations from the planned schedule events, Week 1 will have Cycle 1 of avelumab and trabectedin. Week 3 will have Cycle 2 of avelumab, Week 4 will have Cycle 2 of trabectedin, Week 5 will have Cycle 3 of avelumab, Week 7 will have Cycle 4 of avelumab and Cycle 3 of trabectedin, etc. This may change based on dose delays or modifications. Weeks should be counted sequentially regardless of what number the dose of each agent is.

	Week											
Drug	1	2	3	4	5	6	7	8	9	10	11	12*
Avelumab	•		•		•		•		•		•	
Trabectedin	•			•			•				•	

*Response assessment.

8.0 SUBJECT EVALUATION

8.1 Screening Evaluations

This study will be conducted at the Fred Hutchinson Cancer Research Center, Seattle, USA. Each subject who enters into the screening period for the study receives a unique subject identification number before any study-related procedures are performed. The subject identification number will be assigned. This number will be used to identify the subject throughout the clinical study and must be used on all study documentation related to that subject.

The subject identification number must remain constant throughout the entire clinical study; it must not be changed after initial assignment, including if a subject is rescreened.

Before subjects may be entered into the study, the site must obtain written IRB/IEC approval for the protocol, informed consent form, and all other subject information and/or recruitment material, if applicable. A signed and dated Institutional review Board (IRB) approved informed consent form (latest approved version) must be obtained from each subject prior to performing any study-specific procedures. All subjects or legally authorized representatives must personally sign and date the consent form

before commencement of study-specific procedures. Adverse events are to be collected for a subject once they have signed informed consent through 90 days after the End of Treatment visit.

Screening evaluations will be performed for all subjects to determine eligibility. These evaluations must be obtained \leq 28 days prior to C1D1. Efforts should be made to complete screening procedures as close to initiation of protocol therapy as possible. Standard of care evaluations done prior to signing of consent may be used if they fall within the specified window prior to starting treatment.

A subject is considered enrolled when the investigator decides that the subject has met all eligibility criteria and upon completion of an eligibility review packet. The investigator is to document this decision and date, in the subject's medical record and/or in/on the electronic case report form (eCRF). Subjects should initiate treatment within 7 days of being enrolled to the study, and within the 14 day screening window from time of informed consent.

The following procedures are to be completed during the screening period, after signed informed consent has been obtained, designated in the Schedule of Assessments found in **Appendix C**.

- Informed Consent
- Demographics and Medical History
- Complete Physical Exam and ECOG performance status evaluation
- Vitals Signs, including height and weight
- Electrocardiogram (ECG) (Phase 1 Portion Only)
- Serum Pregnancy Test – For Women of Childbearing Potential only (WCBP)
- Hematology:
 - White blood cell (WBC) count with differential, absolute neutrophil count (ANC), red blood cell (RBC) count, hemoglobin, hematocrit, platelet count, PT/PTT, and INR
- Clinical chemistry and liver function:
 - Sodium, chloride, potassium, glucose, blood urea nitrogen (BUN), creatinine, calcium, AST, ALT, total bilirubin, alkaline phosphatase, lactic acid dehydrogenase, total protein, albumin, amylase, lipase
- Creatine Kinase (CK)
- Thyroid panel:
 - Total T3, Free T4, and thyroid stimulating hormone.
- Urinalysis:
 - Protein, glucose, blood, leukocytes, nitrites, urobilinogen, bilirubin, pH, specific gravity, and ketones.
- Tumor imaging, by CT or MRI
- Echocardiogram or MUGA
- Archival Tissue Collection (if available, this does not have to be obtained prior to C1D1)

8.2 On-Study Clinical Evaluations

A subject is considered on treatment on study day 1 when protocol defined therapy is first administered. Day 1 Avelumab is to be administered after all other protocol-specified pre-dose assessments have been performed during each visit that is required. Subjects will continue therapy until the completion of planned course of treatment, disease progression, or unacceptable AEs. Subjects should be instructed to immediately inform the treating investigator of an AEs. Clinical evaluations take place according to the Study Calendar (**Appendix C**).

Subjects on the Phase I portion of the trial should be evaluated as described below every week for the first 6 weeks and then on all weeks the subject is receiving treatment. Subjects on the Phase II portion of the study are evaluated as described below on weeks that they have treatment, prior to treatment. Every effort should be made to keep the schedule within \pm 3 days from the exact date the subject should be scheduled.

The study calendar will be managed in Weeks, with each dose of each drug being noted by a Cycle. For example, assuming there are no deviations from the planned schedule events, Week 1 will have Cycle 1 of avelumab and trabectedin. Week 3 will have Cycle 2 of avelumab, Week 4 will have Cycle 2 of trabectedin, Week 5 will have Cycle 3 of avelumab, Week 7 will have Cycle 4 of avelumab and Cycle 3 of trabectedin, etc. This may change based on dose delays or modifications. Weeks should be counted sequentially regardless of what number the dose of each agent is.

The following assessments will be performed on each treatment visit, unless otherwise specified:

- Tumor and Symptom-Directed Physical Exam and ECOG performance status evaluation
- Vitals Signs, including weight
- Urine or Serum Pregnancy Test – For Women of Childbearing Potential only (Only on days where avelumab is given as treatment, either alone or in combination with trabectedin. Screening pregnancy test must be serum pregnancy.)
- Hematology:
 - White blood cell (WBC) count with differential, absolute neutrophil count (ANC), red blood cell (RBC) count, hemoglobin, hematocrit, platelet count
- Clinical chemistry and liver function:
 - Sodium, chloride, potassium, glucose, blood urea nitrogen (BUN), creatinine, calcium, AST, ALT, total bilirubin, alkaline phosphatase, lactic acid dehydrogenase, total protein, albumin
- Creatine Kinase (to be drawn on days of trabectedin infusion and as clinically indicated)
 - If trabectedin dosing schedule is modified to every 5 weeks or more at the discretion of the investigator, then the creatine kinase draw will be modified to follow the same schedule.
- Thyroid panel:
 - Total T3, Free T4, and thyroid stimulating hormone (on weeks 1, 7, and every 6 weeks thereafter on a treatment day [+/- 7 days], and at discontinuation)
- Correlative Studies Blood Collection (See **Section 19.3** for schedule)
- Tumor imaging (every 12 weeks).
 - Subjects will have their first post-treatment scan during week 12 and every 12 weeks after that. Additional imaging may be ordered if clinically indicated. All routine care scans ordered for clinical indication should be reviewed via RECIST 1.1.
- Echocardiogram or MUGA (Week 6, then every 12 weeks while receiving trabectedin, beginning with week 18)
- Adverse Event and Concomitant Medication collection and review
- Correlative Studies Blood Collection

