4.0 TRIAL OVERVIEW

4.1 Study Design

4.1.1 Introduction

This is a Phase I/II, non-randomized, open-label, interventional study of avelumab combined with trabectedin for subjects with advanced L-type sarcoma.

The Phase I stage will evaluate trabectedin (1.5 mg/m²) combined with avelumab (800 mg flat dose). Dose reduction for the trabectedin therapy is permitted after the first cycle. Events which would require a dose reduction of trabectedin are outlined in Section 10, however additional dose reductions may be made at the discretion of the treating clinician down to a lowest possible dose of 1 mg/m². There will be no dose escalation or re-escalation of trabectedin.

4.1.2 Definition of dose limiting toxicity (DLT):

During the phase I portion of the protocol, a DLT will be defined as any grade 3 or higher adverse events, at least possibly-related to protocol therapy, which occur during the first 6 weeks of treatment, with the following specifications and limitations:

- Lab abnormalities that have no clinical sequelae (e.g. febrile neutropenia from low ANC, bleeding from thrombocytopenias etc.) and resolve to grade 1 or better within 7 days will not be considered a DLT.
- Any elevation in total bilirubin > 2x institutional ULN will be considered a DLT.
- Any elevation in AST and ALT over 8x institutional ULN will be considered a DLT.
- ANC <500/ μ L lasting 5 days or more will be considered a DLT.
- Platelets < 25,000/ μ L (grade 4 toxicity) lasting 5 days or more will be considered a DLT.
- Hemoglobin < 7.0 lasting 5 days or more will be considered a DLT.

Additionally, should any grade 5 toxicity (death) occur that is at least possibly-related to treatment (e.g. not easily otherwise explained; for example: a car accident), this will be considered a DLT. In the event of any grade 5 toxicity, enrollment will immediately be put on hold and a data safety monitoring board (DSMB) meeting will be requested immediately.

All clinically significant grade 3 or higher toxicities will be recorded and presented to the DSMB at scheduled meetings. Expected toxicities are those outlined in [Section 10](#). The DSMB will be specifically instructed to consider whether there are increased frequency of known toxicities and to make recommendations accordingly if appropriate. Section 10 summarizes criteria for required dose adjustments.

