10.3 Toxicity of Trabectedin

Trabectedin is given as standard of care and does have notable toxicities. The following are to be considered expected toxicities of trabectedin:

- Leukopenia (with neutropenia as the predominant component)
- Malaise
- Infection/sepsis
- Transaminase Elevation
- CK elevation
- Bilirubin or Alkaline phosphatase elevation
- Fatigue
- Nausea/vomiting
- Renal toxicity

Rhabdomyolysis is an unusual but well-described toxicity of trabectedin. If rhabdomyolysis is observed in a single case, this should not be considered a DLT but if multiple cases are seen, this must be reviewed by the DSMB.

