16.2 Phase I Design

The primary objective of the Phase I component of this study is to evaluate the safety of avelumab given in combination with trabectedin among subjects with advanced L-type sarcomas. The phase I component of this study will treat 6 subjects (modified 3+3 design) to demonstrate safety of the combination. Dose-limiting toxicities will be defined as unexpected, probably-related toxicities of grade 3 or higher.

The study design is as follows:

6 subjects will be treated initially.

- If 2 or more subjects experience a DLT at any point during the Phase 1 portion, a new cohort will be added, enrolling an additional 6 subjects at a reduced dose of 1 mg/m² trabectedin.
- Should 2 or more of these next 6 subjects at the reduced dose have a DLT, stop and convene DSMB meeting to recommend changes to the protocol.
- If at any time in the study (including those above) 30% of subjects have a DLT, have a DSMB meeting to review specific toxicities. We will re-calculate the percent of subjects who have had a DLT each time there is a new DLT.

If <2 subjects have DLTs on the 1 mg/m² dose level, another Phase I cohort of 6 subjects implemented, re-escalating to 1.2 mg/m² dosing of trabectedin. If <2 DLTs are seen there, that will be the recommended Phase II dose. If 2 or greater DLTs are seen there, the Phase 2 will move forward at the 1.0 mg/m² dose level, after discussion with the DSMB.

Safety analysis will continue through the entire trial, if at any point during the trial 30% of subjects experience a DLT, the trial should halt and convene a meeting of the DSMB.

A total of up to 18 subjects may enroll on Phase 1, and an additional 16 on Phase 2.

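### Scheduled CK in Phase 1 falls only on trabectedin days, so the 6-week DLT window holds one value after treatment starts and, on planned dates, none that informs on the second dose; add CK to the weekly blood already drawn, and reconcile what counts as a DLT

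*Combined protocol and SAP*

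**What the plan says.** **CK schedule.** Section 8.2: "Creatine Kinase (to be drawn on days of trabectedin infusion and as clinically indicated". Appendix C (calendar and footnote 6) agrees. CK is marked at screening, Weeks 1, 4 and 7+, end of treatment and 30 days later, and not in Weeks 2, 3, 5 or 6. The same calendar marks CBC and chemistry in every one of Weeks 1-7, and footnote 13 makes weekly Phase 1 visits mandatory through Week 7.

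**Dosing.** Section 4.1.3: "Trabectedin will be administered every 3 weeks for the first two doses (Week 1 and Week 4". The third trabectedin dose is in Week 7. Section 7.4 lets either drug vary by 3 days around the planned date.

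**DLT definition.** Section 4.1.2 counts "any grade 3 or higher adverse events, at least possibly-related to protocol therapy, which occur during the first 6 weeks of treatment". It exempts laboratory changes only if they have no clinical sequelae and "resolve to grade 1 or better within 7 days will not be considered a DLT". CK is not among the named exceptions. Section 16.2 defines the term differently: "Dose-limiting toxicities will be defined as unexpected, probably-related toxicities of grade 3 or higher".

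**CK elsewhere.** Section 10.3 lists CK elevation among the expected toxicities of trabectedin. It keeps a single case of rhabdomyolysis out of the DLT count, but says "if multiple cases are seen, this must be reviewed by the DSMB". Section 10.4 makes CK above 2.5 x ULN a trigger for trabectedin dose reduction. Section 9.1 restricts which abnormal laboratory values are recorded as adverse events.

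**The concern.** The protocol treats CK as a toxicity that matters: it has an eligibility limit, a dose-reduction trigger and a route to the DSMB. Yet CK is left out of the weekly Phase 1 panel during the weeks in which the dose is judged.

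Two things are at stake. The first is observation. A rise with no clinical signs that appears and settles between draws leaves no trace in the scheduled data, and the period after the second dose is the first chance to see the effect on muscle of repeated dosing. The second is classification. The exemption in Section 4.1.2 turns on recovery within 7 days, and that cannot be judged from values three weeks apart. Any DLT missed for these reasons would make it easier for a cohort to show fewer than 2 DLTs in 6 subjects.

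**Working it through.** The plan gives no figure for this point, so the check is a day count followed by an illustration.

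**1. Calendar days.** Week w starts on Day 7(w - 1) + 1.
- Trabectedin and CK in Weeks 1, 4 and 7 (Sections 4.1.3, 7.4 and 8.2, Appendix C): Days 1, 22 and 43.
- DLT window (Section 4.1.2): 6 x 7 = 42 days, Days 1-42.
- Phase 1 chemistry in Weeks 1-6: Days 1, 8, 15, 22, 29 and 36.

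**2. CK values inside the window.**
- Day 1: Section 8.2 places assessments before the first avelumab infusion, and trabectedin follows avelumab, so this is a baseline value.
- Day 22: 21 days after dose 1 and on the day of dose 2. The protocol does not say outright that this CK precedes the infusion, but a draw on the infusion day says nothing useful about dose 2.
- Day 43: planned one day after the window closes. With the 3-day allowance it can fall on Days 40-46, so it lies inside the window only if the visit is 1-3 days early.

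The result is one scheduled value after treatment starts and none informative for dose 2. The stretch after Day 22 without a scheduled CK is 42 - 22 = 20 days, or 20/42 = 48% of the window.

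**3. The 7-day exemption.** Scheduled draws are 22 - 1 = 21 and 43 - 22 = 21 days apart. A grade 3 rise that lasts more than 7 days but clears before the next draw meets Section 4.1.2 and is not seen. A rise that is seen on Day 22 has no scheduled repeat within 7 days.

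**4. The same event under each DLT definition.** Take a grade 3 CK rise, possibly related, without symptoms, lasting 10 days.

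| Section | Consequence |
|---|---|
| 4.1.2 | A DLT: at least possibly related, and not recovered to grade 1 within 7 days |
| 16.2 with 10.3 | Probably not a DLT: must be unexpected and probably related, and CK elevation is listed as expected |
| 9.1 | Recorded as an adverse event only if it needs intervention, leads to an SAE, or ends or interrupts study treatment or participation |

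**5. With CK in each of Weeks 1-6.** Values after dose 1 fall on Days 8, 15, 22, 29 and 36 (five instead of one). Values after dose 2 fall on Days 29 and 36 (two instead of none). Planned spacing becomes 7 days, which matches the exemption, and a rise on Day 36 is followed by the Week 7 draw on Day 43.

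**6. Illustration of the effect on the 2-of-6 rule.** With n = 6, P(2 or more) = 1 - (1 - p)^6 - 6p(1 - p)^5. The documents give no rate of grade 3 or higher CK elevation, so a true DLT risk of 30% is assumed and the share missed is varied.
- None missed, p = 0.30: 1 - 0.1176 - 0.3025 = 0.580
- 1 point missed, p = 0.29: 1 - 0.1281 - 0.3139 = 0.558
- 5 points missed, p = 0.25: 1 - 0.1780 - 0.3560 = 0.466

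**The case against.** The best reply accepts the day count and disputes the consequence.

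- **CK may not be a DLT at all.** Section 16.2, which also contains the 2-of-6 rule, requires an unexpected, probably related event. Section 10.3 lists CK elevation as expected and keeps even a single case of rhabdomyolysis out of the count. This stands as a limit. Section 4.1.2 points the other way, and the documents do not say which definition governs.
- **Section 9.1 filters laboratory findings.** Some silent elevations found by extra draws would never be recorded as adverse events. This stands in part: the trigger in Section 10.4 may amount to an intervention, so not every case is excluded. It does mean that more assays alone do not settle the count.
- **Unscheduled draws are allowed.** Section 8.2 permits CK on clinical indication and does not limit that to symptoms. The weekly examination and chemistry (AST, ALT, LDH, creatinine, potassium) could prompt a draw. This stands for suspected cases. It does not cover a CK rise that nothing else signals.
- **A Week 7 value can still count.** It may fall inside the window if the visit is early, and Section 16.2 counts DLTs throughout Phase 1. The first depends on chance scheduling. The second comes with the definition under which CK elevation is least likely to qualify.

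A reader might go further and infer that the schedule biases the dose decision toward acceptance. The documents do not support that. It would require that CK events count as DLTs, that they occur often enough to matter, and that clinically prompted draws miss them. The first is contradictory in the text, and nothing is given for the other two.

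**Conclusion.** The gap in measurement is established from the calendar: one scheduled CK after treatment starts and, on planned dates, none informative for the second dose, with intervals three times as long as the recovery rule they would have to serve. This concerns scheduled draws only; it would be wrong to read it as saying that CK cannot be measured in those weeks.

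The consequence for dose selection is not established. The direction is clear if CK events count as DLTs, since missed events can only make fewer than 2 of 6 easier to reach. The size is unknown. The range of 0.58 down to between 0.56 and 0.47 rests on an assumed 30% risk and an assumed 1 to 5 points missed, and it applies only under the Section 4.1.2 reading. If Section 16.2 governs, most or all of that effect disappears, though the extra values would still serve the trigger in Section 10.4 and the DSMB review in Section 10.3.

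This is a worthwhile, inexpensive improvement in ascertainment, not a demonstrated error in the Phase 1 decision rule.

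**What to change.** 1. In Section 8.2 and Appendix C (calendar row and footnote 6), add CK for Phase 1 subjects to the blood already drawn in Weeks 2, 3, 5 and 6. Phase 2 can stay as written.
2. Reconcile Sections 4.1.2, 9.1, 10.3 and 16.2, so that it is stated whether, and on what terms, a CK elevation is recorded as an adverse event and counted as a DLT. Which definition should prevail is for the sponsor to decide.
3. State how the added values relate to the CK trigger in Section 10.4, which names no time of measurement.

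**Cost.** Four assays per Phase 1 subject: 4 x 6 = 24 for one cohort, and 4 x 18 = 72 if all three cohorts enroll. There is no extra visit and no extra venipuncture. The downside is that some transient elevations without symptoms will be found and must be classified, both against the DLT definition and against the trigger in Section 10.4.
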